# 1. Title and Objective

#### Title:

"Effects of Ericksonian Hypnotherapy Versus Cognitive Behavioral Therapy on Prolonged Grief Among University Students: A Randomized Clinical Trial"

## **Objective:**

The objective of this study is to compare the efficacy of Ericksonian Hypnotherapy (EH) and Cognitive Behavioral Therapy (CBT) in reducing prolonged grief symptoms among university students in Istanbul. Prolonged grief is characterized by an intense longing and emotional distress related to a loss that extends beyond typical bereavement, impacting mental health and daily functioning. By evaluating the effectiveness of EH, a flexible therapeutic approach using indirect suggestion and metaphoric techniques, against the structured approach of CBT, the study aims to identify a potentially effective and culturally adaptable intervention for young adults coping with prolonged grief.

This study will address the following primary research question:

• Does Ericksonian Hypnotherapy provide a more effective reduction in prolonged grief symptoms than Cognitive Behavioral Therapy among university students?

Secondary research questions include:

- How do these interventions affect depressive symptoms associated with prolonged grief?
- Can EH offer a culturally sensitive therapeutic alternative in diverse university settings?

## 2. Study Design

# **Type:**

This is a randomized controlled trial (RCT) employing an expertise-based parallel group design to evaluate the effects of Ericksonian Hypnotherapy (EH) and Cognitive Behavioral Therapy (CBT) on prolonged grief symptoms among university students. Participants are randomly assigned to one of three groups: (1) Ericksonian Hypnotherapy, (2) Cognitive Behavioral Therapy, or (3) a Waitlist Control group.

## **Groups:**

- 1. **Ericksonian Hypnotherapy (EH) Group**: Receives 8 weekly sessions of EH, delivered by a certified therapist specializing in Ericksonian methods.
- 2. **Cognitive Behavioral Therapy (CBT) Group**: Receives 8 weekly sessions of CBT, focusing on structured techniques to address grief-related thoughts and behaviors.
- 3. **Waitlist Control Group**: Does not receive any therapeutic intervention during the study period. After study completion, participants are provided information on available grief support services.

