## **Sample Size:**

A total of 39 participants are recruited and distributed equally across the three groups (13 per group). The sample size was determined based on preliminary data indicating a moderate effect size, with an allocation ratio of 1:1:1 to ensure balanced group representation.

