#### 4. Interventions

#### **Intervention Groups:**

Both intervention groups participate in weekly therapy sessions lasting approximately 60 minutes each over the course of 8 weeks. The two interventions—Ericksonian Hypnotherapy (EH) and Cognitive Behavioral Therapy (CBT)—are administered by therapists specialized in their respective methods, ensuring that each approach is implemented with expertise and consistency.

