# **Consistency in Intervention Delivery:**

To maintain intervention fidelity, both EH and CBT sessions are conducted using standardized session outlines. Both interventions span eight sessions, as previous studies indicate this duration effectively allows for meaningful therapeutic impact without undue burden on university students. Each therapist follows a session-by-session manual to ensure consistency in approach while allowing for individualized adaptation based on the participant's unique grief experience.

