# **Statistical Analysis**

- **Descriptive Statistics**: Descriptive statistics will summarize the demographic characteristics of participants and provide baseline data on grief and depressive symptoms for each group. Mean, standard deviation, and percentage values will be reported for categorical and continuous variables.
- **Primary Analysis**: Repeated measures ANOVA will be conducted to examine the effects of each intervention (EH and CBT) across the three time points (baseline, midpoint, post-intervention) on the primary outcome measure (PGS) and secondary outcome measure (BDI). This analysis allows for the comparison of changes in grief and depressive symptoms within and between groups over time.
- Post-Hoc Comparisons: Following significant ANOVA results, post-hoc pairwise
  comparisons will be conducted to determine specific differences between time points and
  intervention groups. This analysis will help identify any statistically significant improvements
  in grief and depressive symptoms from baseline to midpoint and from midpoint to postintervention.
- Effect Size Calculation: Cohen's d will be calculated to quantify the effect size of EH and CBT interventions on grief and depressive symptoms, providing insights into the practical significance of each therapeutic approach.

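### Therapist is nested within arm but absent from the analysis, so the EH–CBT result cannot be generalised beyond the therapists used without further allowance

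*Combined protocol and SAP*

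**What the plan says.** The Type paragraph of Section 2 describes a trial "employing an expertise-based parallel group design". Section 4 (Intervention Groups) says both therapies are "administered by therapists specialized in their respective methods", so each provider belongs to one arm only. The Groups paragraph describes EH as "delivered by a certified therapist specializing in Ericksonian methods", in the singular. Other places use plural or general wording, for example "Each therapist follows a session-by-session manual to ensure consistency in approach" in Section 4 (Consistency in Intervention Delivery) and the reference to therapists under Risk Management in Section 7. No section gives the number of therapists per arm or says how participants are assigned to them.

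The Statistical Analysis text in Section 6 begins "Repeated measures ANOVA will be conducted to examine the effects of each intervention (EH and CBT" and goes on to the three time points. Pairwise comparisons follow only if the ANOVA is significant. There is no therapist term, cluster adjustment or ICC, and the Sample Size paragraph (39 in total, 13 per arm) makes no allowance for clustering. The primary question in Section 1 is whether EH reduces prolonged grief more than CBT.

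**The concern.** Participants who share a therapist share whatever that therapist adds or takes away, so their outcomes may be correlated. In the EH–CBT contrast the therapist differs wherever the therapy differs. An analysis that assumes independence counts differences between therapists as evidence about the therapies.

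The primary question concerns the therapies, not particular providers. One unusually strong or weak therapist could yield a difference reported as a difference between EH and CBT. Readers could not examine this, because the treating therapist is not among the data the plan says it will collect.

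**Working it through.** **The plan's own figure.** N = 39 cannot be reproduced from the documents: they give no alpha, no power, no numeric effect size and no correlation between visits. One set of assumed inputs gives 39 (three-group by three-time interaction, f = 0.25, correlation 0.5, alpha 0.05, power 0.85). It contains no clustering.

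**Inputs.** From the plan: 13 per arm, therapist nested in arm, no therapist on waitlist, three visits, pairwise tests gated on the ANOVA. Assumed: two-sided 5% tests; therapist ICC 0.01, 0.05 or 0.10; one or two therapists per arm. Baseline precedes randomisation, so the relevant ICC is that of post-baseline or change scores.

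**Step 1. Stand-alone EH–CBT t test, one therapist per arm.** The true standard error exceeds the computed one by the factor √(1 + 13·ICC/(1 − ICC)). The nominal critical value is 2.064 on 24 df, so type I error = 2·P(t₂₄ > 2.064/factor). The nominal half-width is 2.064·√(2/13) = 0.81 within-therapist SD. The plan does not promise an interval, so half-widths apply only if one is reported.

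| ICC | Factor | 2.064/factor | Type I error | Half-width needed (SD) |
|---|---|---|---|---|
| 0.01 | √1.131 = 1.064 | 1.940 | 6.4% | 0.86 |
| 0.05 | √1.684 = 1.298 | 1.590 | 12.5% | 1.05 |
| 0.10 | √2.444 = 1.563 | 1.320 | 19.9% | 1.27 |

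At ICC 0 the factor is 1 and the error is 5%.

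**Step 2. More therapists per arm.** By simulation, the same test at ICC 0.05 has type I error of about 8.3% with two therapists per arm and 6.3% with four.

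**Step 3. The procedure actually planned.** I simulated 40,000 trials per scenario: three groups all measured at three visits, correlation 0.5, and a therapist effect of zero at baseline, half at midpoint and full at post-intervention. The EH–CBT t test (post score or change score) counted only if the group-by-time F test was significant. With one therapist per arm:

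| Scenario | False EH–CBT claim, ICC 0 | False EH–CBT claim, ICC 0.05 |
|---|---|---|
| Neither therapy beats waitlist | about 1% | about 3–6% |
| Both beat waitlist by 0.8 SD | about 2–4% | about 8–10% |

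In each range the lower figure is for the post score and the higher for the change score. When neither therapy beats waitlist, the group-by-time F test itself rejects in about 10% of trials at ICC 0.05, against 5% at ICC 0. With two therapists per arm, the gated rates at ICC 0.05 are about 2–3% and 5–7%.

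**Step 4. What a therapist random effect can deliver.** With J therapists per arm, EH–CBT inference at therapist level has 2J − 2 df. One per arm leaves 0 df, so no test of therapy as such exists. Two per arm leaves 2 df (critical t 4.30). With 6.5 participants per therapist the approximate half-width is 4.30·√(ICC + (1 − ICC)/6.5), or 1.7, 1.9 and 2.1 total SD at ICC 0.01, 0.05 and 0.10.

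**The case against.** Four objections carry weight.

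- **Number of therapists.** A reader might infer from the singular wording in the Groups paragraph that each arm has exactly one therapist. The documents do not support that: the singular can be generic, and the other wording fits one or several. The one-therapist figures are the worst case.
- **Which test.** A reader might take 12.5% or 19.9% as the trial's false-positive rate. They belong to an ungated two-group t test. The planned gate lowers the rate, and where neither therapy beats waitlist it can stay near or below 5% at ICC 0.05. What stands is that each gated rate is still well above its value at ICC 0.
- **Estimand.** A reader might conclude that the planned standard error is simply wrong. It is too small only when the claim extends beyond the therapists used. For a comparison of the therapies as these therapists delivered them, therapist is fixed and the unadjusted standard error is appropriate. That is a narrower question than the one in Section 1.
- **Size of the ICC.** Session manuals and standardised outlines may hold the ICC down. The plan does not measure this, however, and it permits adaptation to the participant ("while allowing for individualized adaptation"), so an ICC of exactly zero is not assured.

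The expertise-based design is a legitimate choice and is not criticised here. The point is that analysis and conclusion should match it.

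**Conclusion.** The point holds in a limited form. The documents establish the nesting, the missing therapist count and the absence of therapist from the analysis. It follows that, read as EH versus CBT in general, the planned test and any interval overstate certainty if therapists differ at all, and that with one therapist per arm no analysis can separate therapy from therapist.

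The size is not established, because it rests on an assumed ICC and therapist count. At ICC 0.05 with one therapist per arm, the ungated error is 12.5% and the gated false-claim rate lies between about 3% and 10%, depending on whether the therapies beat waitlist and which score is compared. At ICC 0.01 the ungated inflation is modest (6.4%), and at ICC 0 there is none. The gated figures also assume that waitlist participants are measured at all three visits. The change is worth making because it is cheap and bears on what the primary comparison can conclude.

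**What to change.** 1. State the number of therapists per arm and how participants are assigned to them. Record the treating therapist for every EH and CBT participant.
2. Keep the planned analysis. Pre-specify a sensitivity table that inflates the EH–CBT standard error for ICC 0.01, 0.05 and 0.10, labelled as the analysis for generalising beyond these therapists. With one therapist per arm the factors are 1.064, 1.298 and 1.563; with more, derive them from the actual caseloads.
3. If both treated arms have several therapists, add as a sensitivity analysis a partially nested mixed model (therapist random effect in the treated arms only) with small-sample degrees of freedom. Fall back to the ICC table if the therapist variance cannot be estimated.
4. If either arm has one therapist, word the conclusion as a comparison of the therapies as delivered by these therapists. The unadjusted standard error serves that claim; the ICC table answers the wider question, and the report should say so.

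The cost is one data field and a short addition to Section 6, with no new staff or participants. The price is a narrower claim and wider sensitivity intervals. With two therapists per arm the mixed-model interval would be very wide (about 2 df), which is why it is not proposed as the primary analysis.

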## **Sample Size:**

A total of 39 participants are recruited and distributed equally across the three groups (13 per group). The sample size was determined based on preliminary data indicating a moderate effect size, with an allocation ratio of 1:1:1 to ensure balanced group representation.

## **Randomization and Allocation Concealment:**

Participants are randomly assigned to one of the three groups using a computer-generated randomization sequence to ensure unbiased group allocation. Allocation concealment is maintained by using sealed envelopes for group assignments, opened only by the treatment providers at the start of each intervention.

## **Blinding:**

While therapists and participants cannot be blinded to the intervention due to the nature of the therapies, outcome assessors are blinded to group assignments to reduce detection bias during assessments.

#### **Duration:**

The total study duration for each participant is 8 weeks, with interventions taking place once a week. Follow-up assessments are conducted after the fourth session (midpoint) and immediately after the eighth session (post-intervention).

#### 3. Participants

#### **Inclusion Criteria:**

Participants must meet the following criteria to be eligible for the study:

• University students aged 18–29 years.

- Ability to communicate and comprehend English proficiently.
- A self-reported experience of significant loss within the past year and symptoms consistent with prolonged grief (as indicated by the Prolonged Grief Scale).
- Willingness and ability to attend weekly therapy sessions for 8 weeks and complete all required assessments.

#### **Exclusion Criteria:**

To ensure a focused study population, participants will be excluded if they meet any of the following criteria:

- Currently undergoing psychopharmacological treatment or psychotherapy for any psychological condition.
- Diagnosed with any major psychological disorder other than prolonged grief as assessed by the SCL-90 Symptom Checklist.
- Inability to commit to the full duration of the study, including weekly sessions and follow-up assessments.
- History of severe psychiatric disorders or significant medical conditions that could interfere with participation in a therapeutic setting.

#### **Recruitment Process:**

Participants are recruited through university networks, social media, and campus advertisements targeting students who have experienced a significant loss. Interested students complete an initial online screening questionnaire, including the SCL-90 and a sociodemographic form, to determine preliminary eligibility. Eligible students are then contacted for a brief interview to confirm their eligibility based on the full inclusion and exclusion criteria.

## **Screening and Baseline Assessment:**

Following confirmation of eligibility, participants complete a baseline assessment, including the Prolonged Grief Scale (PGS) and the Beck Depression Inventory (BDI), administered in a confidential and controlled setting. This baseline assessment provides initial data on grief and depressive symptoms to be compared throughout the study.

#### 4. Interventions

#### **Intervention Groups:**

Both intervention groups participate in weekly therapy sessions lasting approximately 60 minutes each over the course of 8 weeks. The two interventions—Ericksonian Hypnotherapy (EH) and Cognitive Behavioral Therapy (CBT)—are administered by therapists specialized in their respective methods, ensuring that each approach is implemented with expertise and consistency.

## 1. Ericksonian Hypnotherapy (EH) Group:

This group undergoes a tailored EH intervention focusing on the use of indirect suggestion, metaphors, and personal storytelling. Key components of EH include:

o **Initial Sessions (1-2)**: Establishing therapeutic rapport and identifying personal strengths and inner resources related to the participant's grief experience.

- o **Mid-Sessions (3-5)**: Use of guided imagery and metaphoric language to facilitate connection with the loss in a way that promotes healing and acceptance.
- Later Sessions (6-8): Reframing the loss through narrative techniques that encourage integration of the loss into one's life story, fostering resilience and a sense of meaning beyond the grief. The EH sessions aim to engage the unconscious mind, using the participants' personal associations and stories to aid in processing grief in a supportive, non-directive manner.

## 2. Cognitive Behavioral Therapy (CBT) Group:

The CBT intervention is structured and manualized, addressing maladaptive thoughts and behaviors associated with prolonged grief. The key components of the CBT sessions include:

- o **Initial Sessions (1-2)**: Psychoeducation on the CBT model and grief, focusing on the relationship between thoughts, emotions, and behaviors in response to loss.
- Mid-Sessions (3-5): Identifying and challenging grief-related maladaptive thoughts, practicing gradual exposure to situations or reminders of the deceased, and developing coping skills to manage emotional responses.
- Later Sessions (6-8): Emphasis on rebuilding life goals, re-engaging in meaningful activities, and reinforcing coping strategies to foster a renewed sense of purpose and engagement with life. The structured nature of CBT provides participants with concrete tools and cognitive restructuring techniques to process grief and mitigate its impact on daily functioning.

## **Control Group (Waitlist):**

Participants in the control group are placed on a waitlist and do not receive any form of intervention during the study period. Upon study completion, they are offered information on grief counseling resources to ensure they have access to supportive options.

# **Consistency in Intervention Delivery:**

To maintain intervention fidelity, both EH and CBT sessions are conducted using standardized session outlines. Both interventions span eight sessions, as previous studies indicate this duration effectively allows for meaningful therapeutic impact without undue burden on university students. Each therapist follows a session-by-session manual to ensure consistency in approach while allowing for individualized adaptation based on the participant's unique grief experience.

# 5. Outcome Measures

#### **Primary Outcome Measure**

• **Prolonged Grief Scale (PGS)**: The primary outcome measure is the Prolonged Grief Scale (PGS), a validated tool for assessing the intensity and severity of prolonged grief symptoms. The scale consists of 13 items measuring symptoms such as persistent yearning for the deceased, emotional pain related to the loss, and difficulty accepting the reality of the death. Each item is rated on a Likert scale, providing a quantifiable grief score for each participant. This scale is administered at baseline, midpoint (after the fourth session), and post-intervention (after the eighth session) to track changes in grief severity over time. Higher scores indicate more intense grief symptoms.

## **Secondary Outcome Measure**

• Beck Depression Inventory (BDI): The secondary outcome measure is the Beck Depression Inventory (BDI), a 21-item self-report questionnaire widely used to assess the severity of depressive symptoms. The BDI measures various aspects of depression, including sadness, pessimism, loss of interest, and fatigue. Each item is scored on a scale from 0 to 3, with higher scores indicating greater depressive symptomatology. Like the PGS, the BDI is administered at baseline, midpoint, and post-intervention to evaluate any changes in depressive symptoms alongside grief processing.

# **Screening Measure**

• Symptom Checklist-90 (SCL-90): The SCL-90 is used solely as a screening tool before participants are enrolled in the study. This 90-item checklist assesses a broad range of psychological symptoms and provides a Global Severity Index (GSI) to identify individuals with significant psychological distress. Only participants meeting the inclusion criteria, including low levels of distress on the SCL-90, are enrolled to minimize confounding factors.

#### **Data Collection Schedule**

- 1. **Baseline Assessment**: PGS, BDI, and SCL-90 are administered to eligible participants prior to randomization.
- 2. **Midpoint Assessment**: PGS and BDI are re-administered after the fourth session to evaluate initial therapeutic progress.
- 3. **Post-Intervention Assessment**: Final assessment of PGS and BDI scores takes place after the eighth session, allowing for comparison of pre- and post-intervention symptom levels.

# **Data Handling and Confidentiality**

All data collected from participants are anonymized and stored securely in a password-protected database accessible only to the research team. Participants' confidentiality is strictly maintained throughout the study, with data identified solely by randomized participant codes.

## 6. Data Collection and Analysis

#### **Data Collection Process**

- **Baseline Assessment**: After eligibility is confirmed, participants complete the baseline assessment, including the Prolonged Grief Scale (PGS), Beck Depression Inventory (BDI), and Symptom Checklist-90 (SCL-90). These baseline scores establish the initial levels of grief, depression, and overall psychological distress.
- **Midpoint Assessment**: After the fourth session, participants in both the Ericksonian Hypnotherapy (EH) and Cognitive Behavioral Therapy (CBT) groups complete the PGS and BDI. This interim assessment evaluates changes in grief and depressive symptoms, allowing for preliminary comparisons of therapeutic progress.
- **Post-Intervention Assessment**: Upon completion of the eighth and final session, participants complete the PGS and BDI once more. This final assessment enables an analysis of the overall effect of each intervention on grief and depressive symptoms.

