## **Handling Missing Data**

For any missing data due to participant non-completion of assessments, multiple imputation methods will be applied to reduce bias. The study will follow an intent-to-treat approach, analyzing all participants as randomized to their initial groups to maintain the study's validity and statistical power.

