## **Informed Consent**

Informed consent is obtained from all participants prior to their enrollment in the study. The consent form details the study's purpose, procedures, potential risks, and benefits. Participants are informed of their voluntary participation status, confidentiality safeguards, and their right to withdraw from the study at any time without consequences.

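### EH and CBT participants who stop therapy early have no scheduled final PGS/BDI, so the intent-to-treat analysis must rely on imputed outcomes for them

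*Combined protocol and SAP*

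**What the plan says.** Four places give the timing of the post-baseline PGS and BDI, and all four count sessions.

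- **2. Study Design, Duration** puts the midpoint after session 4 and the last assessment right after session 8. Its only calendar statement is "The total study duration for each participant is 8 weeks".
- **5. Outcome Measures, Primary Outcome Measure** gives the same two session markers for the PGS. Secondary Outcome Measure names the midpoint and post-intervention for the BDI without defining them further.
- **5. Outcome Measures, Data Collection Schedule**: "Final assessment of PGS and BDI scores takes place after the eighth session".
- **6. Data Collection and Analysis, Data Collection Process**: "After the fourth session, participants in both the Ericksonian Hypnotherapy (EH) and Cognitive Behavioral Therapy (CBT) groups complete the PGS and BDI", and for the final assessment: "Upon completion of the eighth and final session, participants complete the PGS and BDI once more".

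No section gives an assessment week, a visit window, an early-termination assessment, or follow-up of participants who stop therapy but would still answer questionnaires.

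Handling Missing Data then commits the trial to intent-to-treat: "The study will follow an intent-to-treat approach, analyzing all participants as randomized to their initial groups". Assessments that are not completed are to be multiply imputed. The imputation model is not described. Under Statistical Analysis, the primary method is repeated measures ANOVA over baseline, midpoint and post-intervention.

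**The concern.** Followed as written, the schedule makes the primary outcome in the two therapy arms depend on completing therapy. A student who stops after session 5 has a midpoint score but no scheduled final score. One who stops after session 3 has nothing scheduled after baseline. A repeated measures ANOVA in its usual form needs all three time points, so these students enter the analysis only through imputed values.

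In EH and CBT, the final scores that inform the imputation come only from session-8 completers. If students stop because therapy is burdensome or is not helping, and this is not fully visible in their earlier scores, the imputed values will be too favourable. The comparison with waitlist then flatters therapy. The EH-CBT comparison, which is the primary question, tilts toward whichever therapy loses more students. Scores that were never collected cannot be recovered at the analysis stage.

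**Working it through.** **The plan's own figures.** Sample Size gives 13 per group in three groups: 3 x 13 = 39, which is consistent. No dropout rate is stated anywhere, so the size of the problem cannot be derived from the documents. Everything below that uses a stopping rate or an outcome gap is an assumption.

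**Step 1: what is scheduled, by when an EH or CBT participant stops.**

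| Last session attended | Midpoint PGS/BDI scheduled | Final PGS/BDI scheduled |
|---|---|---|
| 1 to 3 | no | no |
| 4 to 7 | yes | no |
| 8 | yes | yes |

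**Step 2: how likely is at least one unscheduled final score?** There are 2 x 13 = 26 therapy participants. With an assumed stopping probability q, the chance of at least one is 1 - (1 - q)^26.

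- q = 5%: expected number 26 x 0.05 = 1.3; chance 0.74
- q = 10%: expected number 2.6; chance 0.94
- q = 20%: expected number 5.2; chance 0.997

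**Step 3: bias.** Let p1 and p2 be the fractions stopping in the two therapies. Let g be the amount, in SD units, by which the true final scores of those who stop are worse than their imputed scores, after the imputation has used whatever was observed. With the same g in both arms:

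- bias in EH versus CBT = (p1 - p2) x g
- bias in one therapy arm versus waitlist = p1 x g, if the waitlist mean carries no similar bias

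Assume p1 = 3/13, p2 = 1/13 and g = 0.4 to 0.8. Each person is 1/13 = 7.7% of an arm.

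- EH versus CBT: 2/13 = 0.154; 0.154 x 0.4 = 0.06 and 0.154 x 0.8 = 0.12 SD, in favour of the arm with more stopping
- Higher-dropout arm versus waitlist: 3/13 = 0.231; 0.231 x 0.4 = 0.09 and 0.231 x 0.8 = 0.18 SD
- Equal stopping (p1 = p2): the EH-CBT bias is zero, while the bias against waitlist remains
- Observed final scores in the higher-dropout arm: 13 - 3 = 10

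**Step 4: check by simulation, with different assumptions.** Take 13 per arm, completers improving by 0.8 SD, stoppers keeping none or half of that gain, and final scores imputed within arm from baseline by a regression fitted to completers. With 10% versus 30% stopping, the formula gives 0.8 x 0.2 = 0.16 SD and 0.8 x 0.5 x 0.2 = 0.08 SD. The simulated EH-CBT bias was also 0.16 and 0.08 SD. With equal stopping of 10% or 20% it was within 0.003 SD of zero. This imputation did not use midpoint scores, which would shrink the gap where they are informative.

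**Step 5: size against the trial's precision.** With 13 per arm, the standard error of a simple difference between two arms is about sqrt(2/13) = 0.39 SD. The EH-CBT bias in step 3 is therefore 0.06/0.39 = 0.16 to 0.12/0.39 = 0.31 of a standard error.

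**The case against.** The strongest reply is that the documents are silent, not prohibitive. In a plan of eight weekly sessions, after session 8 may be no more than a label for the end-of-treatment visit, and staff could still assess a student who has stopped. Data Collection Schedule uses the label without restricting it to the therapy arms, although waitlist students have no sessions. This is fair: one cannot say that such students would never be assessed. What stands is that no section schedules it, and Data Collection Process words the final trigger as completion of the last session.

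The entry criteria also require willingness and ability to attend and exclude those who cannot commit. That lowers the expected stopping rate but makes no provision for those who stop after randomization.

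Three stronger readings are tempting, and the documents do not support them.

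- **That multiple imputation simply gives stoppers the completers' outcome.** It can condition on baseline and midpoint scores, so a poor early responder can receive a poor imputed value. The model is unspecified and could also borrow from waitlist data. Bias arises only if stoppers do worse than those observed scores predict. If they stop because they have improved, its direction could reverse.
- **That stopping therapy and leaving the study are the same event.** Informed Consent mentions only "their right to withdraw from the study at any time without consequences". That sentence summarizes a right and does not say what happens to assessments when therapy alone stops.
- **That the 8-week duration contradicts the session schedule.** Eight weekly sessions span 7 x 7 = 49 days from session 1. One missed week, made up, gives day 56, which still fits 8 weeks. Only a second missed week takes session 8 to day 63. The plan does not address that contingency, but its sections do not conflict.

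Finally, the assumed EH-CBT bias is less than a third of a standard error. This limits the urgency. It does not remove the case for collecting the scores.

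**Conclusion.** The concern holds as a gap in the assessment schedule. Because both post-baseline assessments are tied to sessions, every planned final score in EH and CBT belongs to a session-8 completer, and the intent-to-treat analysis depends on imputation for those who stop.

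The gap follows from the text; the size of the bias does not. The range of 0.06 to 0.12 SD for EH versus CBT rests on unequal stopping (3/13 versus 1/13) and a residual gap of 0.4 to 0.8 SD. The 0.09 to 0.18 SD against waitlist rests on the same inputs and on an unbiased waitlist mean, but it does not need stopping to be unequal. The point should be fixed, because the remedy is cheap and the lost data cannot be replaced later. It does not by itself invalidate the trial.

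**What to change.** Revise Duration, Primary Outcome Measure, Secondary Outcome Measure, Data Collection Schedule and Data Collection Process together:

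1. Set the midpoint and final PGS/BDI at fixed times with stated windows, the same in all three arms. The sponsor should choose the time anchor and window so that a participant on schedule has had session 8 by the final assessment. The anchor matters: if 8 weeks were counted from randomization, a therapy start more than 56 - 49 = 7 days later would put session 8 past that point even with perfect attendance, unless the window covers it.
2. Collect both questionnaires whether therapy is ongoing, delayed or stopped, unless the participant withdraws consent to assessment.
3. Record the number of sessions attended and the reason for stopping.
4. In Handling Missing Data, state that scores observed after therapy has stopped are used in the intent-to-treat analysis, and that multiple imputation is kept for scores still missing.

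This changes only when outcomes are measured and sets no rule for therapy. The cost is revised wording and a few reminder contacts, with no new instruments or participants. The downside is that some participants with delayed sessions will be assessed before completing all eight, so the estimate reflects therapy as received by that time.
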